8.2 TRIAL CLOSURE

9. STATISTICS AND DATA ANALYSIS

10. MONITORING

GLOSSARY OF ABBREVIATIONS

RCT	Randomised Controlled Trial
GDM	Gestational Diabetes Mellitus

POST-GDM-DNA; Post-delivery intervention for weight loss, glycaemia and cardiovascular health

IRAS ID 292085

Protocol v12.1 8/3/22

CI	Chief investigator
TMG	Trial Management Group
GCP	Good clinical practice
HbA1c	Glycated haemoglobin - monitors average blood glucose
HDL	High-density lipoprotein cholesterol
LDL	Low-density lipoprotein cholesterol
BP	Blood pressure

KEYWORDS

Weight, blood pressure, glycaemia, HbA1c, physical activity, wearable, postnatal, post-delivery, DNA, personalised

STUDY SUMMARY

TITLE Post-delivery intervention in women with previous gestational diabetes mellitus for weight loss, glycaemia and cardiovascular health

DESIGN Feasibility study

Allocation: RCT

AIMS To determine the feasibility of a post-delivery intervention to improve glycemia and cardiovascular function and promote weight loss in women who have had gestational diabetes.

OUTCOME MEASURES Primary outcome; Effect of intervention on HbA1c: difference in HbA1c between intervention arm and control arm measured at 12 weeks.

Secondary Outcomes;

- Adherence to intervention;
- Willingness to be randomised to post-delivery intervention;
- Process measures to evaluate patient experience of study and intervention;
- Participants' preferred time to commence the study, within the start date allowance of 6 weeks – 6 month post-delivery.
- Between-arm differences and within-arm differences to evaluate:
 - Effect of intervention on HbA1c at 12 and 24 weeks
 - Effect of intervention on weight and BMI at 12 and 24 weeks
 - Effect of intervention on systolic and diastolic blood pressure at 12 and 24 weeks
 - Effect of intervention on lipid profile (total cholesterol, HDL, LDL) at 12 and 24 weeks
 - Effect of intervention on physical activity at 12 and 24 weeks

POPULATION We will recruit 50 women aged 18-45 with previous gestational diabetes and randomise them to 1 of 2 arms to commence study at 6 weeks – 6 months post-delivery. Women starting the study at 13 weeks post-delivery will have their routine post-delivery HbA1c act as baseline HBA1c.

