2. STUDY OBJECTIVES

Objectives

To assess:

1. Effect of intervention on HbA1c at 12 and 24 weeks
2. Adherence to intervention
3. Participants’ preferred time to commence the study, within the start date allowance of 6 weeks – 6 month post-delivery.
4. Qualitative data on how participants found post-delivery intervention
5. Effect of intervention on weight at 12 and 24 weeks
6. Effect of intervention on systolic and diastolic blood pressure at 12 and 24 weeks
7. Effect of intervention on lipid profile (total cholesterol, HDL, LDL) at 12 and 24 weeks
8. Effect of intervention on physical activity at 12 and 24 weeks

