3. STUDY DESIGN

We will conduct a feasibility study for an open-label, randomised, controlled trial of a personalised post-delivery intervention (*DNA Nudge*) to improve weight, glycaemia and cardiovascular function in women with previous GDM.

The study is designed to be remote, to enable the study to begin and continue in the pandemic and minimise barriers to recruitment. Study participants will be provided with equipment and instructions to collect samples and measurements at home. Contact with the research team will be over telephone or Microsoft Teams video call.

We will advertise in diabetes antenatal clinics using word-of-mouth, posters, social media and on departmental emails at Imperial College Healthcare NHS Trust or Imperial College POST-GDM-DNA; Post-delivery intervention for weight loss, glycaemia and cardiovascular health IRAS ID 292085

for women with current/previous GDM aged 18-45. We will recruit via Twitter, email and in-person encounters.

We will randomise women to 1 of 2 arms:

Arm 1: Standard dietary and physical activity advice as per NICE guidelines at week 1 (active control arm; n = 25)

Arm 2: DNA-based personalised dietary and physical advice delivered by DNA Nudge dietician at week 1 and by DNA Nudge wearable and app for weeks 1-24 (intervention arm; n = 25)

Women not randomised to DNA Nudge will be provided with an activity app/wearable device (Fitbit) to monitor daily step count. All women will be provided with a home BP monitor and weighing scales.

Week 1

Eligibility assessment, consent, randomisation, IPAQ questionnaire, baseline BP and weight, blood sample collected for baseline lipid profile.

Some women will begin the study at 13 weeks post-delivery and coincide with the routine postnatal HbA1c for women with GDM. The routine post-delivery HbA1c will be baseline HbA1c for this study. For women who commence the study outside the 13 weeks post-delivery window, a finger prick blood sample will be used for a baseline HbA1c test.

Women in the control arm will be given standard dietary and physical activity advice by the research team, in line with NICE guidelines.

Women in the DNA Nudge arm will provide a cheek swab for DNA analysis, carried out by DNA Nudge. They will be given personalised dietary advice by a DNA Nudge dietician, and be provided with DNA Nudge wearable, app and instructions.

Week 6:

Telephone/video-call follow-up to check ongoing willingness to participate and assess adherence.

Week 12:

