Collect weight and BP data from weeks 1-12, collect blood sample for HbA1c and lipid profile. Check ongoing willingness to participate and assess adherence.

Week 18:

Telephone/video-call follow-up to check ongoing willingness to participate and assess adherence.

Week 24:

Collect weight and BP data from weeks 12-24, follow-up IPAQ questionnaire, collect blood sample for HbA1c and lipid profile, return devices and collect usage data from DNA Nudge. Qualitative questionnaire to explore intervention experience.

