6. TREATMENTS

6.1 TREATMENT ARMS

Arm 1: Control group. Women will be supplied with an app/wearable device (Fitbit) to monitor physical activity, weighing scales and a home blood pressure monitor. They will be asked to record their resting blood pressure, resting heart rate and weight twice a week for 24 weeks.

Arm 2: DNA-based intervention. In addition to the BP and weighing procedures for the control group, women will be supplied with a DNA Nudge wearable device and the accompanying app. They will take a cheek swab for genetic analysis and this will be processed in accordance with the manufacturer's guidelines.

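### Physical activity is a stated outcome at 12 and 24 weeks, but the visible schedule has no activity measure common to both arms at week 12

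*Combined protocol and SAP*

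**What the plan says.** Section 2 (Study Objectives) lists "Effect of intervention on physical activity at 12 and 24 weeks" as its eighth objective. The Study Summary repeats it among the secondary outcomes, under the lead-in "Between-arm differences and within-arm differences to evaluate". Two time points are therefore stated, each with comparisons between and within arms.

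Section 3 (Study Design) sets out the contacts. Week 1 comprises "Eligibility assessment, consent, randomisation, IPAQ questionnaire, baseline BP and weight, blood sample collected for baseline lipid profile". Week 12 comprises "Collect weight and BP data from weeks 1-12, collect blood sample for HbA1c and lipid profile", plus a check on willingness to continue and an assessment of adherence. Week 24 includes "follow-up IPAQ questionnaire, collect blood sample for HbA1c and lipid profile, return devices and collect usage data from DNA Nudge".

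On devices, Section 3 says "Women not randomised to DNA Nudge will be provided with an activity app/wearable device (Fitbit) to monitor daily step count". Section 6.1 also lists the Fitbit under the control arm. For home recording it says of the control group "They will be asked to record their resting blood pressure, resting heart rate and weight twice a week for 24 weeks", and of the intervention arm "In addition to the BP and weighing procedures for the control group, women will be supplied with a DNA Nudge wearable device", together with its app.

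**The concern.** An outcome stated at two time points needs data collected at both, and a between-arm comparison needs the same measure in both arms. The visible week-12 entry provides neither for physical activity.

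The consequences are modest but real. Personalised physical advice is part of the intervention, so activity is one of the things it aims to change. Week 12 is also when the primary HbA1c outcome is measured, so activity in the two arms could not be set beside that result on a common scale. With the plan left as it is, the week-12 activity result may be dropped without comment, or replaced after the event by a comparison of Fitbit output in one arm with DNA Nudge output in the other.

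**Working it through.** No arithmetic applies; the check sets the stated outcome against the schedule and the device text.

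**Required** (Study Summary; Section 2): physical activity at week 12 and at week 24, between and within arms.

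**Activity measure scheduled for both arms** (Section 3):

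- Week 1: IPAQ.
- Week 6: none; willingness and adherence only.
- Week 12: none; weight, BP, HbA1c, lipids, willingness and adherence.
- Week 18: none; willingness and adherence only.
- Week 24: follow-up IPAQ.

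Of the two required time points, week 24 is covered and week 12 is not. The week-12 and week-24 entries are built alike: both collect weight, BP, HbA1c and lipids, but only week 24 has the IPAQ.

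**Could another source supply week 12?**

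- *Fitbit.* Sections 3 and 6.1 give it to controls only. No contact includes a download of its data. Step counts, if retrieved, could describe the control arm but could not support a between-arm comparison.
- *DNA Nudge wearable and app.* These are used from week 1 to week 24, with usage data collected at week 24. The text does not say whether usage data include activity, or in what unit.
- *Home records.* Section 6.1 asks for resting blood pressure, resting heart rate and weight. Activity is not among them, and only the BP and weighing procedures are carried over to the intervention arm.
- *Adherence check at week 12.* The same wording appears at weeks 6 and 18, no activity content is given, and adherence is listed as a separate outcome.
- *Section 10.1 (Risk Assessment).* It says that activity-monitoring products are supplied, but gives no arm, time point or measure.
- *Statistics and Data Analysis.* It defines no activity variable and no source for one.

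None of these is a scheduled week-12 activity measure common to both arms. Within-arm change from week 1 to week 12 likewise has no IPAQ value, and would depend on device data whose collection or metric is not specified.

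**The case against.** The strongest reply is that wearables record continuously. The Fitbit may have been given to controls precisely to match tracking that the DNA Nudge wearable already provides, and Section 10.1 does not limit activity monitoring to one arm. Data retrieved at week 24 could then reach back to week 12 with no separate collection. Part of this stands: the documents do not say that the DNA Nudge wearable fails to record activity, and their silence should not be read as absence. But they name no metric for it, no shared unit with the Fitbit and no Fitbit download. The possibility is therefore not a plan for a common week-12 measure.

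The second reply is that Figure 1, titled as the study design, is not shown and could list a week-12 assessment. This stands in full and limits confidence.

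A third is that the matter is small: one time point of one secondary outcome in a 50-woman feasibility study that plans descriptive statistics for its outcomes. That is fair as to weight, but it does not remove the mismatch.

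Two stronger readings are tempting. A reader might infer that no activity data of any kind will exist for week 12; the device text leaves that open. A reader might also infer, from the version date of 8/3/22 and the study end of 1/9/22, that a given share of women are already past week 12. The documents give no actual start dates, so no such share can be calculated.

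**Conclusion.** The mismatch holds on the visible text. Physical activity is stated at weeks 12 and 24, and only week 24 has an activity measure scheduled in both arms. The size is one of two time points for one secondary outcome: the week-12 between-arm comparison has no common scheduled measure.

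The IPAQ at weeks 1 and 24 leaves the week-24 comparison possible, so it would be wrong to conclude that the activity outcome as a whole cannot be assessed.

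The finding assumes that Figure 1 adds no week-12 activity measure and that no unstated metric is shared by the two devices. Confidence is medium, and the point should be corrected before reporting.

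**What to change.** 1. Check Figure 1. If it already shows a week-12 activity measure, add that measure to the week-12 text in Section 3.
2. Otherwise, count how many women still have their week-12 contact ahead.
3. For those women, add the IPAQ to the existing week-12 contact in both arms, and name the IPAQ as the physical activity instrument in the Study Summary and Section 2.
4. If few remain, either report the available week-12 IPAQ descriptively with the number per arm, or restrict the stated outcome to week 24 in both places and disclose this as a change to a stated outcome.
5. Describe device data within arm only, unless the same metric is available in both arms.

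The cost of adding the IPAQ is a few minutes of participant time per questionnaire, at most 50 in all (25 per arm in two arms), using an instrument already in the study. Restricting the outcome adds no data collection but gives up the week-12 result.

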4. PARTICIPANT ENTRY

4.1 PRE-RANDOMISATION EVALUATIONS Women replying to our adverts will be assessed for eligibility by questionnaire.

4.2 INCLUSION CRITERIA Pregnant women with gestational diabetes (women will be given the option to start the study between 6 weeks and 6 months post-delivery) or women who have given birth in the last 12 months and had gestational diabetes during that pregnancy, aged 18-45, access to a smartphone with an operating system of iOS 9.0 or above, or Android 5.0 or above [CB: operating systems correct as of 23/03/21]

4.3 EXCLUSION CRITERIA Diabetes outside of pregnancy (diagnosis of type 1 or 2 diabetes; or HbA1c 48 mmol/mol or above). Health contra-indications to moderate-vigorous exercise. Planning pregnancy during the study period or become pregnant during the study period. Cancer, kidney disease, liver disease, or pancreatitis. Have had gastric bypass surgery or similar weight loss surgery.

4.4 WITHDRAWAL CRITERIA If women withdraw consent or become pregnant during the study period, the data collected to that point will be retained, they will be withdrawn from the study and we will request permission to collect safety outcomes from them.

If they agree to participate, consent will be gained and stored in the site file.

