Buccal mucosal cells samples from the inner side of the cheek and the oral cavity of the participant will be processed in a small genetic testing device (NudgeBox). The end-to-end processing of the sample includes inserting the swab sample into the disposable cartridge, placing the cartridge in the NudgeBox and extracting DNA from the swab sample (a process that can be controlled by the participant's mobile device), amplifying DNA, and analysing genetic results. The sample-containing cartridge is single use only and is disposed upon completion of the test. The genetic analysis, carried out by the NudgeBox, will not examine the whole genetic sequence of the participant, but will be focuses on isolated partial genetic information (i.e. single-nucleotide polymorphism SNPs) that will give us an insight in how a participant is metabolises food, how different nutrients affect his/her body, and what impact different ingredients have on the participant in the long term. To the best of our knowledge, the genetic results provided by our test will not be informative enough to trace the personal details of an individual; furthermore, we will not perform any test to trace personal details. The genetic results, which are encrypted and protected by the password set by the participant, will be stored in the participant's mobile device App. The genetic results are also anonymised, encrypted, and backed-up in a password-protected and secure cloud service (i.e. AWS) maintained by DnaNudge when the mobile device is connected to the internet. The genetic results are separated from other data POST-GDM-DNA; Post-delivery intervention for weight loss, glycaemia and cardiovascular health

IRAS ID 292085

Protocol v12.1 8/3/22

in cloud storage and are secured by password-protected mechanism in which only the user can access his/her own results through the App using his/her log-in and participant ID.

If a participant would like to have all their data deleted, their account will be deleted in the cloud and they will not be able to access their App. All their data (such as genetic results and shopping records) and the back-up will be deleted in the cloud.

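### The experience questionnaire and DNA Nudge usage data are planned only for women who reach week 24, so both may look too favourable if dissatisfied or low-use women leave more often

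*Combined protocol and SAP*

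**What the plan says.** Adherence and participants' experience are objectives 2 and 4 in section 2. Both are also secondary outcomes in the Study Summary, where experience appears as "Process measures to evaluate patient experience of study and intervention".

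Section 3 sets the collection times:

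- **Week 6:** "Telephone/video-call follow-up to check ongoing willingness to participate and assess adherence". Week 18 has the same content.
- **Week 12:** weight, blood pressure and blood results are gathered, and the entry ends "Check ongoing willingness to participate and assess adherence".
- **Week 24:** "return devices and collect usage data from DNA Nudge. Qualitative questionnaire to explore intervention experience".

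For women who leave, section 4.4 covers withdrawal of consent and pregnancy: "the data collected to that point will be retained, they will be withdrawn from the study and we will request permission to collect safety outcomes". Section 8.1 says that women lost to follow-up are flagged and taken out of the study. It does not say whether their earlier data are kept.

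Section 11.3 allows a participant to have her account deleted on request: "All their data (such as genetic results and shopping records) and the back-up will be deleted in the cloud". The statistics section describes a descriptive analysis and gives no analysis set, denominator or missing-data rule for these outcomes.

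**The concern.** The stated aim is feasibility, so whether women use the intervention and how they find it are central results. The only experience instrument described, and the only scheduled retrieval of recorded device usage, both fall at the last visit. A woman who withdraws at week 10, for example, would have a week 6 adherence assessment on file. She would have no questionnaire and no scheduled usage retrieval, and section 4.4 would ask her only about safety.

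Women who leave because the app, wearable or advice did not suit them are among the most informative for a feasibility study. If they are over-represented among leavers, usage and experience reported from those who stay will be more favourable than in the whole arm. The loss may also be permanent: section 11.3 provides for account deletion on request and describes no export beforehand.

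**Working it through.** **Step 1. What is planned for whom.** This sets the schedule in section 3 beside the exit rules in sections 4.4 and 8.1.

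| Item | When collected | Woman who leaves before week 24 |
|---|---|---|
| Experience questionnaire | Week 24 only | None planned |
| DNA Nudge usage data | Week 24 only | No retrieval planned |
| Adherence assessment, method not stated | Weeks 6, 12, 18 | Kept up to exit under 4.4; 8.1 is silent |
| Safety outcomes | Requested at withdrawal or pregnancy | With permission |

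The first two rows show the gap. The third shows that adherence overall is not confined to women who complete.

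**Step 2. How large the effect could be.** The plan gives no figure to reproduce here. Its only relevant number is 25 women in the intervention arm (section 3 and the statistics section). Everything else below is assumed: the number of leavers, 80% mean use in women who stay, and 20%, 50% or 80% in leavers.

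Formula: use over all randomised = (stayers × use in stayers + leavers × use in leavers) / 25. Bias = use in stayers minus use over all randomised.

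With 5 leavers (20 stayers):

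- leavers at 20%: (20 × 0.80 + 5 × 0.20) / 25 = 17 / 25 = 68%, bias 12 points
- leavers at 50%: (16 + 2.5) / 25 = 74%, bias 6 points
- leavers at 80%: (16 + 4) / 25 = 80%, bias 0

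Varying the number of leavers:

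| Leavers of 25 | Leavers' use 20% | Leavers' use 50% | Leavers' use 80% |
|---|---|---|---|
| 3 | 72.8% (bias 7.2) | 76.4% (bias 3.6) | 80% (bias 0) |
| 5 | 68% (bias 12) | 74% (bias 6) | 80% (bias 0) |
| 10 | 56% (bias 24) | 68% (bias 12) | 80% (bias 0) |

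**Step 3. Bounds with no assumption about leavers.** Suppose usage were summarised as yes or no against some threshold (the plan sets none) and 16 of 20 stayers met it, 80%. Over all 25 the proportion lies between 16/25 = 64% (no leaver met it) and (16 + 5)/25 = 84% (all did). With 12 of 15 stayers meeting it, also 80%, the bounds are 12/25 = 48% and (12 + 10)/25 = 88%.

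**The case against.** The strongest case on the other side has four parts.

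- **Adherence is measured before week 24.** A reader might infer that adherence as a whole is known only for women who complete. The documents do not support that. There are three earlier assessments, and section 4.4 says that "the data collected to that point will be retained". This stands, and it confines the point to the questionnaire and the recorded usage. It does not close the gap, because weeks 6 and 18 are calls, no adherence measure is defined at any contact, and usage retrieval is listed only at week 24.
- **Stopping the device is not leaving the study.** Section 4.4 applies to withdrawal of consent and to pregnancy, and section 11.2 speaks separately of withdrawing from protocol treatment. A woman who puts the wearable aside but stays in follow-up would reach the week 24 collection. This stands: the gap concerns women who leave the study.
- **Usage may still be retrievable.** The app and wearable run throughout, and deletion happens only on request. Whether usage logged but not yet exported counts as already collected is unclear. That is a reason to settle it in the text; no earlier retrieval is described.
- **The direction is not certain.** A reader might infer that the results are bound to be too favourable and that a decision on a full trial would rest on them. Neither follows. Pregnancy need not be related to acceptability, there is no bias if leavers resemble stayers, and the plan contains no progression rule. Nor does it specify a satisfaction proportion, since the questionnaire is qualitative, so no percentage bias in satisfaction can be calculated.

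**Conclusion.** The point holds in a limited form. Followed as written, the plan yields questionnaire data and device-recorded usage only from women who reach week 24, and nothing elsewhere in the document repairs this. Adherence more broadly has earlier, though undefined, assessments.

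The consequence is a possible upward bias in usage and experience, conditional on dissatisfied or low-use women leaving more often. Under the assumptions shown for usage, with 5 leavers of 25, it is 12 points at the wider contrast, 6 at the narrower and zero if leavers are like stayers. The documents give neither a dropout rate nor any usage figure, so these numbers illustrate scale and are not estimates. Without assuming a direction, 5 missing women still leave a 20-point range (64% to 84%) on a yes/no usage measure. The change is worth making because it is cheap and bears directly on objectives 2 and 4.

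**What to change.** - **Section 3, weeks 6, 12 and 18:** export DNA Nudge usage to date at the contact already scheduled, and state how adherence is assessed there.
- **Section 4.4:** the plan already says "we will request permission to collect safety outcomes from them". Extend that request to the same experience questionnaire, remote and optional, and to a usage export before any account deletion.
- **Section 8.1:** state that data already collected, and usage exported to date, are kept for women lost to follow-up. A questionnaire is seldom practical for women who cannot be reached.
- **Statistics section:** report usage and adherence with all women randomised to the intervention arm as the denominator, give the number with data, and show leavers separately for usage and experience.

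The cost is a data export at existing contacts, one remote questionnaire at exit and a sentence in the consent information. Some leavers will decline, so the gap will narrow but not close.
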